10.6.4.2. CKD Progression**CKD Progression****40% eGFR Decline**

- 40% eGFR decline is determined by the eGFR values provided by the central laboratory.
- Confirmed 40% decline in eGFR from baseline (confirmed 4 – 13 weeks later): If confirmatory eGFR value obtained 4 – 13 weeks following the initial eGFR value that also exhibits a 40% decline from baseline, then the initial 40% eGFR decline is considered a confirmed 40% decline in eGFR. This is required for the principal secondary analysis of CKD progression. If this confirmatory eGFR value does not exhibit a 40% decline from baseline, is outside of the 4 – 13 week window, or is missing, then the subject does not meet the requirement for this component of the CKD progression endpoint.
- Single 40% decline in eGFR from baseline: If a confirmatory eGFR value does not exist within the 4-13 week window after the initial 40% decline in eGFR from baseline, then this initial 40% decline in eGFR is considered a single 40% decline.

Dates for Non-Adjudicated Components of CKD Progression

- Confirmed 40% decline in eGFR from baseline (confirmed 4 – 13 weeks later): date of initial eGFR assessment that showed at least 40% decline from baseline
- Single 40% decline in eGFR from baseline: date of the single 40% decline in eGFR from baseline
- For the supportive analysis of CKD progression on probable eGFR decline, the single 40% decline in eGFR from baseline will be included. The date of a 40% decline in eGFR from baseline will be set to the earlier date of a confirmed decline date and a single decline date, if both are present.
- Chronic dialysis: dialysis initiation date where duration of dialysis \geq 90 days
- Kidney transplantation: date of kidney transplant

Dates for Adjudicated Components of CKD Progression

- Chronic dialysis: event date provided by the CEC. Note that chronic dialysis includes both dialysis less than 90 days with expected chronicity and dialysis indicated for chronic condition but not provided.

For purposes of adjudication rate summaries, the following dates will be used as investigator-reported dates for the adjudicated components of the chronic dialysis CKD progression component:

- Chronic dialysis < 90 days: Dialysis start date from the Indication for Dialysis eCRF form
- Not initiating chronic dialysis when indicated: Date that dialysis was indicated from the Indication for Dialysis eCRF form

Missing or Partial Endpoint Dates

- Use guidance in other subsections in Section [10.6.4](#) where applicable.

CKD Progression								

 If dialysis start dates are missing or partial for subjects who started dialysis, they will be imputed using the dialysis indication dates. If dialysis stop dates are missing or partial for subjects whose “Dialysis stopped prior to 90 days”, they will be imputed using min(dialysis start date + 90 days, dialysis start date of next record – 1). 								
Order of CKD Progression Components								

 If multiple CKD progression component events occur on the same day or have imputed dates that place them on the same day, but it is not clear which event occurred first, then the following order will be applied: 
 CKD Progression: Confirmed 40% eGFR Decline (or single 40% eGFR decline for supportive analysis) CKD Progression: Chronic Dialysis CKD Progression: Kidney Transplant Death 								
Investigator-reported Events for Adjudication Rates								

 Adjudication rates will be reported for two component events of the CKD progression chronic dialysis component: chronic dialysis < 90 days and not initiating chronic dialysis when indicated. For subjects with a baseline eGFR ≥ 15 mL/min/1.73m² and an investigator-reported event date \geq randomization date, the following definitions will be used to identify investigator-reported events: 
  
 Event	Definition of CKD Progression	
   
 Chronic dialysis <90 days	Indication for Dialysis records with a total dialysis duration = ‘stopped prior to 90 days’	
 
 Dialysis duration unknown	Indication for Dialysis records with a total dialysis duration = ‘unknown (e.g. study completed, withdrawn consent, LTFU)’	
 
 Not initiating chronic dialysis when indicated	Indication for Dialysis records where Was dialysis initiated = ‘No’	
  
	Event	Definition of CKD Progression	Chronic dialysis <90 days	Indication for Dialysis records with a total dialysis duration = ‘stopped prior to 90 days’	Dialysis duration unknown	Indication for Dialysis records with a total dialysis duration = ‘unknown (e.g. study completed, withdrawn consent, LTFU)’	Not initiating chronic dialysis when indicated	Indication for Dialysis records where Was dialysis initiated = ‘No’
Event	Definition of CKD Progression							
Chronic dialysis <90 days	Indication for Dialysis records with a total dialysis duration = ‘stopped prior to 90 days’							
Dialysis duration unknown	Indication for Dialysis records with a total dialysis duration = ‘unknown (e.g. study completed, withdrawn consent, LTFU)’							
Not initiating chronic dialysis when indicated	Indication for Dialysis records where Was dialysis initiated = ‘No’							
General Definitions								

 Use guidance in Section 10.6.4. 								

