In the situation that there is a fatal MI (or fatal stroke, hospitalization for heart failure, or pulmonary embolism) that does not have both an MI (or stroke, hospitalization for heart failure, or pulmonary embolism) endpoint and a death endpoint reported, the date of the event that is reported will be used in the analysis of all relevant endpoints. This would additionally apply to situations where the MI (or stroke, hospitalization for heart failure, or pulmonary embolism) may occur within an analysis period and the death may occur outside of the analysis period; the endpoint with the date in the analysis period will be used for all relevant endpoints.

Missing or Partial Endpoint Dates

Missing or Partial Event (Start) Dates

- If event dates are missing or partial and there is not sufficient information to classify the time period of the event, the event will be classified as occurring on-treatment and post-randomization. The event will also be considered to have occurred during the follow-up for cardiovascular events as defined in Section 10.6.4.
- The following rules for missing or partial event dates for events other than death will be implemented as long as the imputed date is after the randomization date. If the imputed date is prior to the randomization date, then the date of randomization will be imputed for the event date.
 - If only the day of the month is missing, impute the first day of the month (e.g., --FEB2016 would impute as 01FEB2016)
 - If the month and day of the month are missing, impute 01JAN (e.g., ----2016 would

CV Safety Endpoints

- impute as 01JAN2016)
 - If the year, month, and day of month are missing, impute the randomization date
- The following rules for missing or partial death dates will be implemented as long as the imputed date is after the randomization date. If the imputed date is prior to the randomization date, then the date of randomization will be imputed for the death date.
 - The latest clinic visit, telephone visit, other contact with subject visit, CV endpoint (other than death), AE or SAE date, or date last known to be alive will be determined. If the year, month, and day of month of the death are missing then the death date will be imputed as the latest of the dates.

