
 • eGFR will be calculated automatically by the central laboratory using the CKD Epidemiology Collaboration (CKD- EPI) for all subjects 
CKD – EPI: $GFR = 141 \times \min(S_{cr}/k, 1)^\alpha \times \max(S_{cr}/k, 1)^{-1.209} \times 0.993^{Age} \times 1.018 \text{ [if female]} \times 1.159 \text{ [if black]}$ where: S_{cr} is serum creatinine in mg/dL, k is 0.7 for females and 0.9 for males, α is -0.329 for females and -0.411 for males, min indicates the minimum of S_{cr}/k or 1, and max indicates the maximum of S_{cr}/k or 1.
 
The demographic information used by the central laboratory for the calculation of eGFR (i.e., gender and race) will be reconciled with the demographic information contained in the eCRF to ensure consistency.

Laboratory Parameters

 • The collected lab values of eGFR, creatinine(serum), chloride(serum), UACR, 24 hour urine collection (sodium, aldosterone and creatinine), if any, will not be used in the following scenarios: 
 ○ For subjects who had a kidney transplant, these lab values taken after the kidney transplant date will not be used. ○ For subjects who started dialysis (dialysis ≥90 days, dialysis <90 days with positive adjudication, dialysis started but duration unknown), these lab values taken after the dialysis start will not be used. ○ For subjects who started dialysis (dialysis <90 days with negative adjudication), these lab values taken during the dialysis period will not be used.
Normal Range Categories, PCI Criteria Categories and Worst Case Values

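### A partial dialysis start date is replaced by the indication date even when the recorded month or year differs, which can misdate non-adjudicated chronic dialysis and drop valid eGFR values (minor)

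*SAP*

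**What the plan says.** SAP section 10.6.4.2, under missing or partial endpoint dates, opens with a pointer: "Use guidance in other subsections in Section" 10.6.4, limited to where that guidance applies. It then gives a rule for dialysis: "If dialysis start dates are missing or partial for subjects who started dialysis, they will be imputed using the dialysis indication dates". Wholly missing and partial dates are treated alike.

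Two other provisions depend on the start date:

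- **Event date (10.6.4.2).** For non-adjudicated dialysis, the event date is given as "Chronic dialysis: dialysis initiation date where duration of dialysis" is at least 90 days. For adjudicated dialysis the entry is different: "Chronic dialysis: event date provided by the CEC".
- **eGFR cut-off (10.6.4.5).** For subjects who started dialysis of 90 days or more, shorter dialysis that was positively adjudicated, or dialysis of unknown duration, "these lab values taken after the dialysis start will not be used".

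The general rule for partial event dates other than death, in section 10.6.4.1, keeps what was recorded: "If only the day of the month is missing, impute the first day of the month", and "If the month and day of the month are missing, impute 01JAN".

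**The concern.** Indication and initiation are separate items on the Indication for Dialysis form. The SAP even counts dialysis that was indicated but never started. The two dates can therefore lie months apart. When the start month or year is known and the indication falls outside it, the rule replaces recorded information with a date that contradicts it.

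Time to CKD progression is one of the four principal secondary analyses tested by the Holm-Bonferroni procedure (section 10.11.1.2), and its components are also analysed one by one (section 8.2.2.2). A wrong start date can move the chronic-dialysis event. It can also remove an eGFR value on which the 40% decline component depends, and the eGFR change and slope analyses lose the same values.

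**Working it through.** The SAP gives no figure for this rule, so there is nothing to reproduce. The check sets the rules side by side and then works through assumed dates.

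**Comparison with the SAP's other partial-date rules**

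| Item | Section | Treatment of a partial date |
|---|---|---|
| Last non-zero dose, treatment stop, study completion | 10.6.1 | Anchor date used only if it falls in the recorded month or year; otherwise month end or year end |
| AE start and stop | 10.7.2.1 | Anchor date used only if it falls in the recorded month or year; otherwise first or last day of the period |
| CV events other than death | 10.6.4.1 | First day of the recorded month or year, not before randomization |
| Dialysis start | 10.6.4.2 | Indication date, with no condition |

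Only the dialysis rule lets the anchor override the recorded period.

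**Example 1: event date.** Assume dialysis was indicated on 15 Jan 2019, the start was recorded as `--APR2019`, and dialysis lasted 90 days or more, so the case is not adjudicated.

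- Date under the rule: 15 Jan 2019.
- Earliest true start, 1 Apr: 16 + 28 + 31 + 1 = 76 days later.
- Latest true start, 30 Apr: 76 + 29 = 105 days later.
- The event is dated 76 to 105 days too early. Under the 10.6.4.1 convention it would be 1 Apr, which is 0 to 29 days early.

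**Example 2: only the year recorded.** Assume indication on 10 Jan 2019 and a start recorded as `----2020`.

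- Under the dialysis rule the date is 356 days too early (true start 1 Jan 2020) to 721 days too early (31 Dec 2020).
- Under the 10.6.4.1 convention (1 Jan 2020) it is 0 to 721 − 356 = 365 days early.

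**eGFR exclusion, using the dates of Example 1.** All eGFR from 16 Jan to the true April start is ignored, although the subject was not yet on dialysis. A 40% decline counts only if it is confirmed 4 to 13 weeks (28 to 91 days) later. In year 1, clinical chemistry is scheduled at Weeks 4, 16, 28, 40 and 52, so the next scheduled value comes 12 weeks (84 days) on.

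Suppose a first 40% decline is seen *d* days before 15 Jan, and the scheduled value 84 days later shows it again.

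- The confirming value falls 84 − *d* days after 15 Jan.
- For *d* = 9 to 83 this is 75 down to 1 days after 15 Jan, so it precedes even a 1 April start.
- The rule discards it. If no other value confirms the decline, that component is not met.
- The composite event then moves from 15 Jan − *d* to 15 Jan, which is *d* days (9 to 83) **later**.

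The rule can therefore shift the composite in either direction.

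**The case against.** **The wording may be softer than it looks.** The pointer to the rest of section 10.6.4 brings in month-preserving rules, and imputing by means of the indication date could mean filling in only the missing parts. But the dialysis sentence is specific and names partial dates, and nothing limits it to the missing parts. In Example 1 that reading gives 15 April, which is 76 + 14 = 90 days after the date from full replacement. Two programmers could defensibly produce either.

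**Early dating is this SAP's habit, and indication is clinically meaningful.** Section 10.6.4.1 also dates early: to 1 January if only the year is known, and to randomization if nothing is. It would therefore be wrong to say that the general rule errs by at most 30 days; that is so only when just the day is missing. ESRD here also includes dialysis that was indicated but not started. This supports the indication date when the start is wholly missing. It does not support overriding a recorded month or year.

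**Many records are untouched.** This stands. Adjudicated dialysis takes the endpoint committee's date. An earlier confirmed eGFR decline can leave the composite time unchanged. Little or nothing is lost when the indication falls in the recorded month close to the true start. The supportive analysis that accepts a single 40% decline would still count an unconfirmed one. The rule is the same in both arms.

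**A stronger reading a reader might infer** is that a backdated start lengthens a short course of dialysis to 90 days or more, so that it counts without adjudication. The SAP does not support this. Section 10.6.4.2 identifies dialysis under 90 days from the duration category entered on the Indication for Dialysis form, and no section derives the class from stop date minus start date. The stop-date rule uses the same category as its condition and can set the stop at start plus 90 days, which would defeat a date-derived class. Such a case stays in adjudication and, if positive, takes the committee's date.

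**Conclusion.** The point holds in limited form and is minor. As written, the rule can contradict a recorded month or year of dialysis start. It can misdate non-adjudicated chronic dialysis, and for subjects who started dialysis it can exclude valid eGFR values between indication and true start, including one needed to confirm a 40% decline.

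For the assumed case of a January indication and an April start, the dialysis event is 76 to 105 days too early. The size of the error is not limited by the recorded month or year. It is not unlimited either, because follow-up is finite.

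A reader might infer that CKD progression is generally dated too early. That does not follow: a lost confirming value makes the composite later, and an earlier confirmed decline leaves it where it was.

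The verdict rests on reading the rule as replacing the whole date, and on applying the section 10.6.4.5 exclusion to the 40% decline as well as to the eGFR analyses. The number of partial start dates is not given and may be small, so no effect on the hazard ratio or the Holm test can be claimed.

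**What to change.** Replace the sentence in section 10.6.4.2 with:

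> If the month and year (or only the year) of dialysis start are recorded, use the dialysis indication date only if it falls in that month (or year). Otherwise use the first day of the recorded month (or year), or the last contact at which the subject was known not to be on dialysis if that is later and falls within the recorded month (or year). Use the indication date alone only when the start date is wholly missing.

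The text deliberately does not require the start to be on or after the indication date. With a start recorded in March and an indication in April, that bound would again contradict the recorded month. In Example 1 the imputed start becomes 1 April 2019, or a later dialysis-free contact in April.

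It would also help to say that the 90-day class is read from the eCRF duration field, since the event-date entry does not say how the duration is obtained.

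The cost is a few lines of SAP text and a small programming change, best made before unblinding. No new data are needed.

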
 CKD progression is defined as (see Section 10.6.4): 
 40% decline in eGFR from baseline (confirmed 4 – 13 weeks later) or; End stage renal disease (ESRD) as defined by either: 
 Initiating chronic dialysis for ≥ 90 days*, or Not initiating chronic dialysis when dialysis is indicated (adjudicated), or Kidney transplantation 
*Adjudicate only if the duration of dialysis is <90 days.
 For purposes of summary and analysis, the components of CKD progression include: 
 Confirmed 40% eGFR decline Chronic dialysis. The chronic dialysis component includes subjects who initiate chronic dialysis for ≥ 90 days (non-adjudicated), positively adjudicated cases of dialysis less than 90 days with expected chronicity, and positively adjudicated cases where dialysis was indicated for a chronic condition but not provided. Kidney transplant Summaries and Analysis of CKD progression and its components will be restricted to the subset of subjects with baseline eGFR ≥ 15 ml/min/1.73m². Due to the presence of all-cause mortality as a competing risk, analysis of time to progression of CKD will be performed using Fine and Gray's subdistribution hazards analysis model, adjusting for the same factors as the co-primary MACE analysis (Section 7.2.2) for the evaluation of superiority. 
 For supportive purposes, the Cox Proportional Hazards model used in the co-primary MACE analysis will also be run. Analysis will include only the CKD progression events occurring within the time period for follow-up of CV endpoints as described in Section 10.6.4. For the components of CKD progression intended to go through the adjudication process, only the adjudicated results will be used.
Model Results Presentation

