10.6.3.4. RBC and Whole Blood Transfusion Endpoints

Number of RBC and Whole Blood Transfusions	

 • The number of transfusions associated with each RBC and Whole Blood Transfusion record is determined by the frequency, start date, end date and number of units, as described below. • Only on-treatment transfusions are included. “End date” below refers to the end date defined for the transfusion, or the end of the on-treatment period, if sooner (see Section 10.4.1). • For records with a frequency of “Once only” or “Continuous infusion”, each record is considered to be a single transfusion (regardless of start and end dates or number of units) • For records with a frequency of “Once daily”, the number of transfusions will equal the duration (end date – start date +1). • For records with a frequency of “PRN”, or where the frequency is unknown, the number of transfusions for each record will be equal to the number of units recorded. • For other transfusion records, the number of transfusions will equal the duration (end date – start date +1) times a multiplier, as defined below: The number of transfusions should be rounded up to the nearest integer. 	
Frequency	Multiplier
QM	0.033
Every 2 weeks	0.071
Once a week	0.14
Q4D	0.25

2 times per week	0.29
Q3D	0.33
3 times per week	0.43
Every other day	0.5
4 times per week	0.57
5 times per week	0.71
BID	2
Q12H	2
TID	3
Q8H	3
QID	4
Q6H	4
5 times per day	5
Q4H	6

Number of RBC and Whole Blood Transfusion Events

- RBC and Whole Blood Transfusion Events are defined by grouping together on-treatment transfusion records.
- Transfusion records are grouped into the same Transfusion Event if the transfusion start/end dates match with or are contained within an Admission/Discharge period, (based on the Hospitalization page in the eCRF).
- For example, the following transfusion records would be grouped into a single Transfusion Event, because each transfusion is contained within the same hospital admission/discharge period:

Dose	Frequency	Transfusion Dates		Hospitalisation		Comment
		Start Date	End Date	Admission	Discharge	
1 unit	Once only	16FEB2019	16FEB2019	15FEB2019	26FEB2019	1 Transfusion Event
1 unit	Once only	19FEB2019	19FEB2019	15FEB2019	26FEB2019	

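### The stop-date imputation for dialysis recorded as ending before 90 days gives 90 or 91 days when no further dialysis record starts within 90 days, and the SAP does not say whether dates or the eCRF category decide the 90-day test

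*SAP*

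**What the plan says.** Section 10.6.4.2, under Missing or Partial Endpoint Dates, limits the rule to one group of records: "If dialysis stop dates are missing or partial for subjects whose “Dialysis stopped prior to 90 days". For these, "they will be imputed using min(dialysis start date + 90 days, dialysis start date of next record – 1").

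The 90-day line matters in two other places. Section 8.2.1.2 defines the component: "The chronic dialysis component includes subjects who initiate chronic dialysis for ≥ 90 days (non-adjudicated"), with the footnote "Adjudicate only if the duration of dialysis is <90 days". Section 10.6.4.2 dates the non-adjudicated event: "Chronic dialysis: dialysis initiation date where duration of dialysis" is at least 90 days. Neither place says where that duration comes from.

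For the adjudication-rate summaries only, Section 10.6.4.2 identifies the short cases from the eCRF response: "Indication for Dialysis records with a total dialysis duration = ‘stopped prior to 90 days".

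Section 10.6.4.5 also depends on the stop date. For dialysis under 90 days with negative adjudication, eGFR, serum creatinine and the other listed values are dropped over the episode: "these lab values taken during the dialysis period will not be used".

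**The concern.** The rule fills in a date for records whose duration is already known to be under 90 days, yet its first term is start plus 90 days. The filled-in value can therefore be one that the record rules out, and it falls at the threshold separating cases reviewed by the endpoint committee from cases counted automatically.

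Time to CKD progression is a principal secondary endpoint tested under the Holm-Bonferroni procedure (Section 10.11.1.2). If a programmer derives duration from the dates, a short, possibly reversible episode would meet the non-adjudicated definition. If the eCRF category is used instead, the imputed date still sets how long eGFR values are discarded after a negatively adjudicated episode. Those values feed the confirmed 40% decline component, the eGFR MMRM and the eGFR slope model.

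**Working it through.** **Inputs.** The imputation rule, its restriction to records marked as under 90 days, and the non-adjudicated event date (Section 10.6.4.2); the 90-day threshold and adjudication trigger (Section 8.2.1.2). No day count is given for dialysis. Elsewhere the SAP counts inclusively, for example for transfusions: "the number of transfusions will equal the duration (end date – start date +1"). Both counts are shown.

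**Step 1: apply the rule as written.** Stop = min(start + 90, next start − 1).

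| Next dialysis record starts | Imputed stop | Stop − start | Inclusive | 90 or more? |
|---|---|---|---|---|
| None, or day +91 or later | start + 90 | 90 | 91 | Yes, both counts |
| Day +90 | start + 89 | 89 | 90 | Inclusive count only |
| Day +89 | start + 88 | 88 | 89 | No |
| Day +60 | start + 59 | 59 | 60 | No |

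A record that ended before 90 days can last at most 89 days. The first row breaks that limit under both counts. The second breaks it only under the inclusive count.

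**Step 2: partial dates.** Take a start of 03MAR and a stop known only to be in March.
- Latest possible stop: 31MAR, which is 28 days by subtraction or 29 inclusive.
- Rule with no early next record: 03MAR + 90 days = 01JUN, which is 90 or 91 days.
- Excess: 90 − 28 = 62 days beyond the latest date the record allows.

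The hospitalization end-date rule in Section 10.6.4.1 handles the same problem differently. It uses the last day of the known month, capped at the day before the next admission or, if there is none, at study completion or withdrawal. The dialysis rule uses neither the known month nor a study-end cap.

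**Step 3: which consequence follows.**
- *Dates decide the 90-day test.* The first-row record meets the non-adjudicated definition and is counted from dialysis initiation.
- *The eCRF category decides.* The record stays in the under-90-day group and goes to adjudication. The imputed date then matters for the laboratory exclusion after a negative adjudication. Year 1 chemistry is scheduled at Weeks 4, 16, 28, 40 and 52 (Section 10.2.1.1), so draws are 12 × 7 = 84 days apart and a 90-day window typically holds about one. From Week 64 the main schedule has chemistry every 24 weeks (168 days), so a 90-day window may hold none.

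**Step 4: a cap that stays under 90.** Start + 89 gives 89 by subtraction but 90 inclusive. Start + 88 gives 88 and 89, below the threshold under either count.

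**The case against.** The strongest reply is that the classification exists before any date is imputed. The rule applies only where the eCRF already says the episode was short, and the adjudication-rate summaries find such cases by that response. The four-way sorting in Section 10.6.4.5 also includes a duration-unknown group, which matches an eCRF response rather than a date calculation. Adjudication is a committee process whose results enter the analysis as inputs; filling in a stop date does not by itself withdraw a case from review. This stands. A reader might infer that the SAP turns short dialysis into unadjudicated CKD progression, but it does not prescribe that. It leaves the source of the duration unstated, and the use of the eCRF category is spelled out only for the summaries.

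Other limits also stand. The rule is a minimum, so a next record by day +89 keeps the duration under 90. The imputed stop date never becomes the event date, which is dialysis initiation or the committee's date. The endpoint analysis includes only subjects with baseline eGFR of at least 15 mL/min/1.73m².

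A reader might also infer that the laboratory exclusion covers nearly the whole 4–13 week (28–91 day) confirmation window. That does not follow: the window runs from the first eGFR value showing the decline, not from dialysis start, so the overlap depends on timing. The visit schedule after transition to dialysis is in a protocol appendix that is not shown. Where a stop date is wholly missing, taking a late date is in line with the SAP's other end-date conventions, so the excess loss of data is clearest for partial dates.

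None of this defends a value that the record excludes.

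**Conclusion.** The rule is wrong as written. With no further dialysis record starting within 90 days, it gives 90 days (91 inclusive) to an episode recorded as shorter, and it disregards a known stop month and the end of the study.

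The consequence depends on a choice the SAP leaves open. If the dates decide, such a case could count as CKD progression without adjudication. If the category decides, the effect is limited to an over-long laboratory exclusion after negatively adjudicated short dialysis, typically about one scheduled Year 1 chemistry draw per affected record. That estimate assumes the nominal main-study schedule.

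The SAP gives no count of records with a missing or partial stop date. The number is probably small, and no effect on the treatment comparison can be calculated. The case for correcting it is that the rule produces an impossible value at a decision threshold and is cheap to repair.

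**What to change.** In Section 10.6.4.2, replace the rule for dialysis recorded as ended before 90 days. Impute a missing or partial stop date as the earliest of:
- the last day of the known month, if the date is partial;
- dialysis start + 88 days;
- the day before the next dialysis record starts;
- the study completion or withdrawal date.

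Add one sentence stating that the eCRF duration category, not an imputed date, decides between the adjudicated and non-adjudicated routes for the chronic dialysis component.

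The cost is about two sentences of SAP text and a one-line programming change. No new data are needed.
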